6.1.3. Clinical Trial Population

40 participants (approx. 20 EDE and 20 non-EDE subjects) will be recruited for the study.

Trial participants will be recruited from the local population at the investigational site. [REDACTED]

[REDACTED]

6.1.4. Trial Duration

This study is a randomized 3-arm comparison of emulsion OM3 eye drops compared to two comparators. Participants will attend a Screening visit (Day -14) and up to 3 scheduled visits for each eye drop. It will take participants

approximately 18 weeks to complete all 3 arms of the study.

Table 5: Visits

Visit Type:	Visit No:	Study Arm
Screening (Day -14)	1	-
Eye Drop #1: Baseline and 15 min assessment	2a	1
Eye Drop #1: 3-5 hour assessment	2b	1
Eye Drop #1: 4 week assessment	2c	1
Eye Drop #2: Baseline and 15 min assessment	3a	2
Eye Drop #2: 3-5 hour assessment	3b	2
Eye Drop #2: 4 week assessment	3c	2
Eye Drop #3: Baseline and 15 min assessment	4a	3
Eye Drop #3: 3-5 hour assessment	4b	3
Eye Drop #3: 4 week assessment and Exit	4c	3

All study participants will attend a Screening visit and receive REFRESH PLUS® for 2 weeks during a run-in period prior to randomization at Visit 2a. After the 4 week assessment, all study participants will undergo a minimum 2 week wash-out period using run-in product REFRESH PLUS® before returning to complete the next arm of the study. These procedures will be repeated until the subjects have completed all 3 arms of the study.

6.1.5. Enrolment

A study participant is considered enrolled when they have signed the Participant Information Statement and Consent Form.

6.2. Primary Endpoint

The primary endpoint is a measurable difference in tear evaporation rate (Vapometer) between the eye drops after initial application (15 min) and/or after 1 hour and/or 4 hours of application and/or after 4 weeks of daily use.

6.3. Secondary Endpoint(s)

Tear break-up time (TBUT) with fluorescein, subjective comfort scores and lipid layer thickness (LipiView).

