1. PROTOCOL SYNOPSIS

Table 1

Protocol Title	A two comparator, controlled phase 3 study of OM3 Tear formulation versus OPTIVE ADVANCED Unit Dose and OPTIVE Unit Dose eye drops in patients with and without evaporative dry eye.
Background	
 ○ The normal tear film is a relatively stable, thin film composed of a superficial lipid layer and an aqueous layer intermixed with a mucous gel layer, which is partially adherent to the corneal and conjunctival surface epithelium ○ Dysfunction of one or more components of the tear film can lead to loss of tear film stability and symptoms of dry eye ○ The majority of patients with dry eye are prescribed artificial tears to alleviate symptoms and maintain a healthy ocular surface ○ OM3 Tear is a new unit dose emulsion, containing flaxseed/castor oil, which is being developed by [REDACTED]. It is desirable to understand the effect that this new emulsion has on tear film evaporation and tear lipid profile via interferometry, in patients with evaporative dry eye (EDE) and those without (non-EDE). It would also be valuable to evaluate the retention time of the lipid components of the new emulsion via tear collection and analysis in EDE and non-EDE patients
Study Design	Single centre, double-masked, randomized, 3 arm comparison of OM3 Tear eye drops to two comparators.
Aims and Objectives	To measure tear film evaporation rate, tear lipid profile via interferometry and tear lipid components before and 15 mins, 1 hour and 4 hours after the first dose, and again after 4 weeks of use of the emulsion OM3 Tear eye drops, compared to two comparators (Optive Advanced Unit Dose and Optive Unit Dose).
Recruitment	September 2016
Study Start & End Dates	September 2016 – April 2017
Sample size	
Up to 40 participants will be recruited (approx. 20 EDE and 20 non-EDE subjects). This sample size was calculated on the basis of detecting a difference in:
 
 ○ tear evaporation rate between the eye drops of 36 gm⁻²/h where the expected standard deviation of the measurement is 50 gm⁻²/h, assuming an estimate of type 1 error $\alpha = 0.05$ and power of 80% for a two tailed test¹
Subject Source	UNSW and general community

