
Visit Schedule – 3 arm study
	
Visit 1 (Day -14): Screening visit, dispensing run-in product (Refresh Plus)
 
ARM 1:
 
Visit 2a (Day 1): Pre-instillation and 15 min (± 5 min) post-instillation assessment - Eye Drop #1
 
Visit 2b (Day 1): 1 hour (± 15 min) post-instillation assessment - Eye Drop #1
 
Visit 2c* (Day 1): 4 hour (± 30 min) post-instillation assessment - Eye Drop #1
 
Visit 3 (4 weeks): 4 week assessment - Eye Drop #1
 
ARM 2: (after minimum 2 week wash-out period using run-in product Refresh Plus)

	
Visit 4a ([6 weeks): Pre-instillation and 15 min (\pm 5 min) post-instillation assessment - Eye Drop #2
 
Visit 4b (6 weeks): 1 hour (\pm 15 min) post-instillation assessment - Eye Drop #2
 
Visit 4c* (6 weeks): 4 hour (\pm 30 min) post-instillation assessment - Eye Drop #2
 
Visit 5 (10 weeks): 4 week assessment - Eye Drop #2
 
ARM 3: (after minimum 2 week wash-out period using run-in product Refresh Plus)
 
Visit 6a (12 weeks): Pre-instillation and 15 min (\pm 5 min) post-instillation assessment - Eye Drop #3
 
Visit 6b (12 weeks): 1 hour (\pm 15 min) post-instillation assessment - Eye Drop #3
 
Visit 6c* (12 weeks): 4 hour (\pm 30 min) post-instillation assessment - Eye Drop #3
 
Visit 7 (16 weeks): 4 week assessment Eye Drop #3
 
Note: Subjects are NOT to instil any eye drops within 3 hours prior to the scheduled visits
 
* 4 hour assessments will only be conducted on participants who are able to attend this additional visit on the same day as the initial assessment

Procedure
	
Standard ocular examination and non-standard ocular examination procedures will be carried out at the scheduled visits.
 
Standard optometric procedures may include:
 
 ○ Subjective questionnaires (OSDI, Likert and VAS) ○ Corneal and conjunctival staining (Fluorescein and Lissamine Green) 
Non-standard optometric procedures may include:
 
 ○ Tear evaporation rate (Modified Vapometer, Delphin Technologies) ○ Tear Break-Up Time (with fluorescein) and lipid layer grade ○ Tear film lipid layer thickness (LipiView Interferometer) ○ [REDACTED] ○ [REDACTED] ○ [REDACTED]

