
Study Endpoints
	
The primary endpoint is a measurable difference in tear evaporation rate between the eye drops after initial application (15 min) and/or after 1 hour and/or 4 hours of application and/or after 4 weeks of daily use.
 
The secondary endpoints are (i) a measurable difference in TBUT between the

	
eye drops after initial application (15 min) and/or after 1 hour and/or 4 hours of application and/or after 4 weeks of daily use and (ii) a measurable difference in symptom improvement between the eye drops after initial application (15 min) and after 4 weeks of daily use.

Statistical Considerations
	
Paired t-tests, repeated measures ANOVA or linear mixed model analysis using Bonferroni adjustment for multiple comparisons and p value set at $p < 0.05$. Mann Whitney U test will be used to compare tear film lipidome between the eye drops.

IRB Status & Details
	
This clinical research study requires approval from the Human Research Ethics Committee at the University of New South Wales prior to study initiation, any advertising, and participant enrolment.
 
 ○ HREC meetings held monthly ○ Lead time for new applications: approx. 2 months

Dissemination of Results
	
 ○ Publication in peer-reviewed journals ○ Presentation at International conferences

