4. BACKGROUND INFORMATION

4.1. Background and Clinical Rationale

The normal tear film is a relatively stable, thin film composed of a superficial lipid layer and an aqueous layer intermixed with a mucous gel layer, which is partially adherent to the corneal and conjunctival surface epithelium. Dysfunction of one or more components of the tear film can lead to loss of tear film stability and symptoms of dry eye. The majority of patients with dry eye are prescribed artificial tears to alleviate symptoms and maintain a healthy ocular surface.

The purpose of this study is to evaluate the retention time of the lipid components of the new emulsion OM3 Tear eye drops via tear collection and analysis in evaporative dry eye (EDE) and non-EDE patients. Tear film evaporation rate, tear lipid profile via interferometry and tear lipid components will be evaluated before and 15 mins, 1 hour and 4 hours after the first dose, and again after 4 weeks of use of the emulsion OM3 Tear eye drops, compared to two comparators (Optive Advanced Unit Dose and Optive Unit Dose).

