5. STUDY OBJECTIVES AND CLINICAL HYPOTHESIS

5.1. *Study Objective*

The objective of this study is to measure tear film evaporation rate, tear lipid profile via interferometry and tear lipid components with the use of the emulsion OM3 Tear eye drops, compared to two comparators (Optive Advanced Unit Dose and Optive Unit Dose) in subjects with EDE and those without (non-EDE)

5.2. *Clinical Hypothesis*

Tear evaporation rate as measured with the Vapometer is better (i.e. lower) with the emulsion OM3 Tear formulation compared to at least one of the two comparators at one or more of the post eye drop instillation time-points.

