6.1. Methodology / Study Visits

6.1.1. Data Requirements per Visit with Visit window (\pm days)

The data requirements for each visit are shown in Table 4.

Table 4

	Visit 1	Visit 2a	Visit 2b*	Visit 2c	Visit 3a	Visit 3b*	Visit 3c	Visit 4a	Visit 4b*	Visit 4c
Timeline	Day - 14	Day 1 #1	Day 1 #1	4 weeks #1	6 weeks #2	6 weeks #2	10 weeks #2	12 weeks #3	12 weeks #3	16 weeks #3
Procedure										
Informed Consent	Y	N	N	N	N	N	N	N	N	N
Inclusion/Exclusion criteria	Y	Y	N	N	N	N	N	N	N	N
Ocular, medical history, medications, demographics	Y	N	N	N	N	N	N	N	N	N
Updated history, symptoms, problems	Y	Y	N	Y	Y	Y	Y	Y	Y	Y
Vision tests	Y	Y	Y	Y	Y	Y	Y	Y	Y	Y
Biomicroscopy (ocular health, staining)	Y	Y	N	Y	Y	N	Y	Y	N	Y
Meibomian gland assessment	Y	N	N	N	N	N	N	N	N	N
Schirmer test (eligibility)	Y	N	N	N	N	N	N	N	N	N
Instill eye drops	Y	Y	N	N	Y	N	N	Y	N	N
Tear evaporation rate	N	Y	Y	Y	Y	Y	Y	Y	Y	Y
Eye photo (ocular surface area)	Y	N	N	N	N	N	N	N	N	N
Schirmer test (tear collection)	N	Y	Y	Y	Y	Y	Y	Y	Y	Y
LipiView	N	Y	Y	Y	Y	Y	Y	Y	Y	Y
TBUT (fluorescein)	N	Y	Y	Y	Y	Y	Y	Y	Y	Y
Questionnaires (OSDI, VAS)	Y	Y	Y	Y	Y	Y	Y	Y	Y	Y

Y = Yes, required information, N = No, not required

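### The synopsis and section 6.3 list different secondary endpoints, and the tear-lipid objective has neither an endpoint nor an analysis that addresses retention

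*Combined protocol and SAP*

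**What the plan says.** **Endpoints.** The primary endpoint measure is the same in the synopsis, section 6 and section 6.2: "The primary endpoint is a measurable difference in tear evaporation rate (Vapometer) between the eye drops". The secondary endpoints are stated twice. The synopsis (Study Endpoints) has two: a TBUT difference at 15 minutes, 1 hour, 4 hours and/or 4 weeks, and "a measurable difference in symptom improvement between the eye drops after initial application (15 min) and after 4 weeks of daily use". Section 6.3 has three, without times, contrasts or instruments: "Tear break-up time (TBUT) with fluorescein, subjective comfort scores and lipid layer thickness (LipiView").

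**Purpose and objective.** Section 4.1 says "The purpose of this study is to evaluate the retention time of the lipid components of the new emulsion OM3 Tear eye drops". The synopsis background ranks this lower: "It would also be valuable to evaluate the retention time of the lipid components of the new emulsion via tear collection and analysis". Section 5.1 does not name retention; its objective is to "measure tear film evaporation rate, tear lipid profile via interferometry and tear lipid components".

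**Symptom instruments.** The synopsis procedure list has "Subjective questionnaires (OSDI, Likert and VAS"). Table 4 has "Questionnaires (OSDI, VAS"). Neither endpoint list names an instrument.

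**Lipid analysis.** The synopsis and section 13.1.3 both assign the lipidome comparison between drops to a Mann-Whitney U test. Neither gives a lipid variable, a time point or a baseline. Table 4 schedules tear collection at every visit after screening.

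**The concern.** Both secondary lists are current text, and they cannot both be followed. After the data are seen, a LipiView result could be reported as secondary by citing section 6.3 or as exploratory by citing the synopsis. The same freedom applies to the symptom result, where improvement suggests a change from a baseline and a comfort score may be a level. Bonferroni adjustment is promised without a defined family, so the choice of list could also affect the threshold applied.

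The lipid question has a different problem. Tears are collected throughout and a lipid test is planned, so a p-value for lipid differences between drops will probably be produced. As specified, it would not say how long OM3 lipid stays on the eye, which section 4.1 gives as the reason for the study.

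**Working it through.** No figure in the documents is attached to a secondary endpoint or to retention, and the sample-size calculation concerns evaporation rate only. The check is therefore a comparison of text.

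**1. The secondary lists side by side.**

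| Item | Synopsis, Study Endpoints | Section 6.3 |
|---|---|---|
| TBUT | Yes, four times | Yes, no times |
| Symptoms | Improvement, at 15 min and 4 weeks | Subjective comfort scores, no times |
| LipiView thickness | Not listed | Yes, no times |
| Tear lipid components or retention | Not listed | Not listed |

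Only TBUT is common to both without a change of meaning. In the synopsis LipiView is a procedure, and interferometry is an aim, but neither is an endpoint.

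**2. Could the lipid endpoint be behind a redaction?** Endpoints are stated in four places: the synopsis, section 6, section 6.2 and section 6.3. None shows a redaction, and none names a tear-lipid component or a retention measure. LipiView does not fill the gap, because sections 9.1 and 11.2 describe it as measuring lipid layer thickness, not the composition of collected tears.

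**3. Does the planned lipid test address retention?** Retention concerns how the lipid level changes after a dose. It needs a pre-instillation value and values at known times afterwards. The stated test compares drops and specifies neither.

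**4. Does the planned lipid test fit the design?** Section 6 randomises the order of the drops, and every participant is to use all three. Values for two drops therefore come from the same people, whereas Mann-Whitney U assumes independent samples. The analogue for means shows the effect. With equal standard deviation σ in each period and within-participant correlation ρ, the variance of a within-participant difference is 2σ²(1−ρ). An unpaired comparison uses 2σ². Positive ρ makes the unpaired test less sensitive than it need be. The documents give no σ or ρ for any lipid measure, so the loss cannot be quantified.

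**5. Do the sampling times support a retention endpoint?** The documents disagree.

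- The synopsis visit schedule and section 6 have pre-instillation, 15 min, 1 hour, 4 hours and 4 weeks.
- Table 4 and Table 5 have a combined baseline and 15-minute visit, one later same-day visit, and 4 weeks. There is no 1-hour assessment.
- The Table 4 key calls the later same-day visit 3–5 hours, while its footnote says 4 hours ± 30 minutes.
- The 4-hour visit is optional in both schedules.
- Table 4 has a single tear-collection entry for the combined visit, so it does not show that both a pre-instillation and a 15-minute sample are taken.

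**6. Is the 4-week value a retention measure?** It follows weeks of as-needed use and, under section 10.1, at least 3 hours without drops. It can reflect continued use, but it does not track one dose over time.

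**The case against.** The strongest reply is that the measurements are planned and only labels are missing. The synopsis aims and section 4.1 commit to measuring tear lipid components before dosing, at 15 minutes, 1 hour and 4 hours, and after 4 weeks. Interferometry is an aim throughout, so LipiView measurement is prespecified on any reading. Section 13.1.3 also lists paired tests and refers to differences between visits. This stands to a degree: a reader might infer that retention is ignored altogether, and the documents do not support that. But a planned measurement is not an endpoint with a variable, a time and a contrast, and where the plan does name a test for the lipidome, it is the unpaired one.

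Second, retention may not be the main purpose, since the synopsis background only calls it valuable as well. That is fair, but it adds an inconsistency. Section 5.1 still makes tear lipid components an objective, and they have no endpoint.

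Third, items are redacted in the synopsis procedures and in sections 9.2, 11.1 and 11.2, including directly after the sentence on comfort questionnaires. The symptom instrument or a lipid assay may be specified there. It therefore cannot be claimed that the instrument is left open in the full document, only that neither endpoint list names it. The two symptom terms may also be intended to mean the same thing, although the text does not say so.

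Finally, a reader might try to count the extra contrasts that one list allows over the other. The documents do not support a single count, because the two schedules differ in their post-dose times and in the number of instruments.

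**Conclusion.** The point holds for the secondary endpoints and for the lipid objective. The two lists have two and three entries. They disagree on whether LipiView is an endpoint and on the wording and timing of the symptom measure. Of the four endpoint statements, none covers tear lipid components or retention, and the one analysis assigned to the lipid data would not answer the retention question in a three-period within-participant design.

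A reader might infer that the primary analysis is compromised too. The documents do not support that on this point, since evaporation rate is the primary measure everywhere it is stated.

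The conclusion assumes that the unredacted endpoint statements are complete and that all three drops are given to the same participants, as section 6 says. This should be corrected before unmasking. It affects which secondary and lipid results can be called prespecified, and no numerical size can be attached to it.

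**What to change.** 1. Put one identical secondary list in the synopsis and section 6.3: TBUT, LipiView thickness, and symptom change from the same period's pre-instillation score, each with stated times. Name one symptom instrument per time point, unless the redacted text already does so.
2. Add a tear-lipid endpoint. Name the lipid variable, and define the endpoint as change from the same period's pre-instillation sample at the same-day post-dose times.
3. Compare OM3 with each comparator within participant by a paired method, for example Wilcoxon signed rank or a mixed model, in place of Mann-Whitney U. The plan already names both methods.
4. Report the 4-week lipid value separately as an effect of continued use, not as retention.
5. Make the rank of retention the same in the synopsis background and section 4.1, and label all other instruments and times exploratory.
6. Before finalising, reconcile the synopsis schedule with Table 4: the 1-hour assessment, the window and optional status of the 4-hour visit, and separate entries for the pre-instillation and 15-minute tear collections.

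The cost is mainly wording, but not only that. Reconciling the schedule may add an assessment or a tear collection to Table 4, and an optional 4-hour visit will leave fewer participants at that time. Fewer results can then be called secondary.

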7. SELECTION AND WITHDRAWAL OF PARTICIPANTS

7.1. Participant Selection

Only subjects who have signs and symptoms of dry eye disease (EDE or non-EDE) will be enrolled.

Participants will be pre-screened for suitability by way of a general phone questionnaire. Informed consent will be obtained prior to any clinical trial procedures.

All participants will conform to the clinical trial entry criteria listed below:

7.1.1. Inclusion Criteria

The following are requirements for entry into the study:

1. Male or female, ≥ 18 years of age;
2. Able to read and comprehend English and give informed consent as demonstrated by signing a record of informed consent;
3. Not wearing contact lenses in the past 3 months before enrolling;
4. Willing to use eye drops and comply with the study visit schedule as directed by the Investigator;
5. Habitual (corrected or uncorrected) visual acuity of 6/9.5 or better in each eye;
6. At the Screening visit (Day -14), patients must have Ocular Surface Disease Index (OSDI) score >18 (0 to 100 scale). At Baseline (Day 1) visits, patients must have OSDI score > 12 to continue in the study;
7. TBUT ≤ 10 sec in at least 1 eye at the Screening visit;
8. Corneal sodium fluorescein staining score ≥ 1 and <4 (Oxford scheme) at screening and baseline visit;
9. If using RESTASIS[®] cyclosporine ophthalmic emulsion, subjects must be using drops for ≥ 3 months prior to Screening.
10. Subjects with primary open-angle glaucoma or ocular hypertension (OHT) may be included provided they are on stable monotherapy bilaterally, with both eyes IOP controlled (≤ 21 mm Hg). Any topical IOP-lowering medications must have a start date of ≥ 3 months prior to Screening date and dosage is not expected to change during the study. The type of medication will be recorded at the Screening visit along with other concomitant medications;
11. Ability to follow study instructions and likely to complete all required visits.

Additional Inclusion Criteria for EDE Classification:

- Tear Evaporation Rate (TER) ≥ 110 (TBC)

Additional Inclusion Criteria for non-EDE Classification:

- Tear Evaporation Rate (TER) < 110 (TBC)

For patients who have one eye meeting EDE criteria, and other eye meeting non-EDE criteria, their Schirmer score will be used to determine the classification. If their Schirmer score is >10 in both eyes, they will be classified in the EDE group.

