
Selection criteria
	
General Inclusion Criteria
 
 ○ Able to read and comprehend English and give informed consent as demonstrated by signing a record of informed consent; ○ Over 18 years of age; ○ Not wearing contact lenses in the past 3 months before enrolling ○ Willing to use eye drops and comply with the study visit schedule as directed by the Investigator; ○ Habitual (corrected or uncorrected) visual acuity of 6/9.5 or better in each eye; ○ At the Screening visit (Day -14), patients must have Ocular Surface Disease Index (OSDI) score >18 (0 to 100 scale). At Baseline (Day 1) visits, patients must have OSDI score > 12 to continue in the study. ○ TBUT≤10sec in at least 1 eye at Screening visit and Baseline visit ○ Corneal sodium fluorescein staining score ≥ 1 and <4 (Oxford scheme) at Screening and Baseline visit. 
Additional Inclusion Criteria for EDE Classification
 
 ○ Tear Evaporation Rate (TER) ≥ 110 - To be confirmed (TBC) 
Additional Inclusion Criteria for non-EDE Classification
 
 ○ Tear Evaporation Rate (TER) < 110 (TBC) 
For patients who have one eye meeting EDE criteria, and other eye meeting non-EDE criteria, their Schirmer score will be used to determine the classification. If their Schirmer score is >10 in both eyes, they will be classified in the EDE group.
 
General Exclusion Criteria
 
 ○ Schirmer test (with anesthesia) ≤ 2 mm in either eye at Screening ○ Patients who are currently using topical ocular medication or have used topical ocular medication within 2 weeks of the Screening visit. Patients who are being treated bilaterally with a marketed artificial tear for dry eye can be considered, provided they discontinue use at the Screening visit; ○ Any active anterior segment disease excluding blepharitis; ○ Any systemic disease that may affect ocular health e.g. Graves disease, and auto-immune diseases such as ankylosing spondylitis, multiple sclerosis and systemic lupus erythematosus; ○ History of epilepsy or migraines exacerbated by flashing, strobe-like lights; ○ Rigid or soft contact lens wearer, including orthokeratology; ○ History of eye surgery within 6 months prior to enrolment in the study; ○ Previous corneal refractive surgery.

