6. STUDY DESIGN

This study is a single centre, double-masked, randomized, 3-arm comparison of emulsion OM3 eye drops compared to two comparators. All study subjects will attend a Screening visit and receive REFRESH PLUS® for 2 weeks during a run-in period prior to randomization. Subjects will be randomized as to the order of allocation to use the OM3 Tear eye drop and the two comparators. For each arm of the study, assessments will be conducted prior to eye drop instillation and 15 min, 1 hour and 4 hours post-instillation. Subjects will then be dispensed with the randomized study eye drop and instructed to instill 1 to 2 drops of their assigned study product in each eye, as needed, but at least twice daily, for 4 weeks. Subjects will attend a 4 week visit assessment and then undergo a minimum 2 week wash-out period using run-in product REFRESH PLUS® before returning to complete the next arm of the study. These procedures will be repeated until the subjects have completed all 3 arms of the study.

The primary endpoint is a measurable difference in tear evaporation rate between the eye drops after initial application (15 min) and/or after 1 hour and/or 4 hours of application and/or after 4 weeks of daily use.

All proposed procedures conform to the NHMRC Statement on Human Experimentation.

Participants are considered enrolled when they have signed the informed consent form and are regarded as part of the clinical trial population.

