 # = eye drop
 a = Baseline and 15 min post-eye drop assessment
 b = 3-5 hour post-eye drop assessment
 c = 4 week post-eye drop assessment

*Visits 2b, 3b and 4b are scheduled 4 hours (± 30 mins) after the corresponding visits 2a, 3a and 4a on the same day, and therefore are not compulsory for all study participants to attend. Only those who are able to attend this visit will complete the assessment visits 2b, 3b and 4b.

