7.3.3. Event Follow-up

If a participant has experienced an adverse event that is continuing at the end of the study participation, the event is marked as ongoing. The Investigator should ensure appropriate follow-up care is arranged/provided to the participant as appropriate.

If an adverse event has occurred and is continuing, the participant should be followed until the event has resolved, or stabilised if there is no chance of improvement. Source notes and the reporting form should be updated as

appropriate, and the information forwarded to the Sponsor/HREC/TGA as necessary.

7.3.4. Whether and How Participants are to be Replaced:

Participants who experience an adverse response during the course of the study, that requires early discontinuation from the study, will not be replaced. Participants who are not suitable at Screening will be replaced, until the enrolment target is reached.

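### As scheduled, the Visit 2a evaporation reading both assigns EDE status and serves as the period-1 baseline, which builds a spurious period-1 change into each group

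*Combined protocol and SAP*

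**What the plan says.** Section 7.1.1 gives the two group definitions as "Tear Evaporation Rate (TER) ≥ 110 (TBC") and "Tear Evaporation Rate (TER) < 110 (TBC"). The Synopsis spells out the abbreviation as "To be confirmed (TBC"). No unit is attached to 110. When a participant's eyes fall on opposite sides of the cut-off, the Schirmer score decides: "If their Schirmer score is >10 in both eyes, they will be classified in the EDE group".

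In Table 4 (section 6.1.1) the row "Tear evaporation rate" is N at Visit 1 (Day -14) and Y from Visit 2a onward. The key under the table describes the a-visits: "a = Baseline and 15 min post-eye drop assessment". Section 6.1.2 places randomisation at Visit 2. Section 6 says that in each arm "assessments will be conducted prior to eye drop instillation and 15 min, 1 hour and 4 hours post-instillation". No other pre-drop TER is scheduled before randomisation. The eligibility Schirmer test and the eye photograph used to calculate absolute evaporation (section 11.2) are both taken at Screening.

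The target is approximately 20 EDE and 20 non-EDE participants (section 13.1.1). On replacement, section 7.3.4 says: "Participants who are not suitable at Screening will be replaced, until the enrolment target is reached".

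**The concern.** A participant who reads above the cut-off on one day does so partly because of true level and partly because of that day's error. If the same reading is then the baseline, the error is expected to be positive in EDE and negative in non-EDE. Later readings do not share that selection, so EDE appears to improve and non-EDE to worsen after whichever drop came first. Periods 2 and 3 have fresh baselines and are not affected.

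This matters because before-after change is part of the plan. The Synopsis aims measure TER before and after the first dose and again at 4 weeks. Section 13.1.3 tests differences between visits and lists paired t-tests. Section 5.1 frames the objective in subjects with and without EDE.

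Two smaller consequences follow. A provisional cut-off with no date for fixing it could be settled after primary-variable readings have been seen. And the site would not know a participant's group until after the run-in.

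**Working it through.** **The plan's own figure.** Section 13.1.1 gives a difference between drops of 36, SD 50, two-sided alpha 0.05 and 80% power. Reading 50 as the SD of a paired difference, the normal approximation is (50 × (1.960 + 0.842) / 36)² = 15.1, so 16. A paired t-test needs 18. That is close to the stated 20 per group. The figure of 36 is therefore a within-person contrast between drops, a different quantity from the one computed below.

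**Inputs.** SD 50 is from section 13.1.1, taken here as the total SD of a TER reading. The cut-off of 110 is from section 7.1.1. The documents give neither the test-retest reliability (ρ) nor the population mean of TER. I assume ρ from 0.8 to 0.5 and, first, a mean at the cut-off.

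**Formulas.**
- Expected chance component of the classifying baseline: (1 - ρ) × 50 × φ(0)/0.5 = (1 - ρ) × 39.9. It is positive in EDE and negative in non-EDE, and the spurious change has the opposite sign.
- Average per drop over three periods, if order is balanced: one third of that.
- Share in the wrong group relative to long-run TER: arccos(√ρ)/π. For the mean of two readings, replace ρ by 2ρ/(1 + ρ).

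| ρ | Period-1 shift in each group (g/m²/h) | Per drop, averaged over 3 periods | Wrong group, one reading | Wrong group, mean of two |
|---|---|---|---|---|
| 0.8 | 8.0 | 2.7 | 15% | 11% |
| 0.7 | 12.0 | 4.0 | 18% | 14% |
| 0.6 | 16.0 | 5.3 | 22% | 17% |
| 0.5 | 19.9 | 6.6 | 25% | 20% |

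The groups move in opposite directions, so the spurious EDE minus non-EDE gap in change is twice the shift: about 16 to 40 in period 1, or about 5 to 13 averaged over periods.

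**Sensitivity.** At ρ = 0.9 the shift is 4.0. With the mean at 90 and ρ = 0.7 it is 16.0 in EDE and 8.4 in non-EDE; with the mean at 130 these swap. Pooled over both groups it cancels. With the mean at 90, for example, 34.5% of participants are EDE: 0.345 × 16.0 = 5.5 and 0.655 × 8.4 = 5.5, with opposite signs.

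**Effect on the drop comparison.** In 10,000 simulated three-period crossovers (40 participants, ρ = 0.7, no drop effect, classification at Visit 2a), mean period-1 change was -11.8 in EDE and +11.9 in non-EDE. Mean period-2 change was about 0. The between-drop difference within EDE was about 0 both on change (-0.2) and on post-drop values (+0.2).

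The precision of that contrast is also unaffected. The SD of the within-EDE between-drop difference in change is the same whether Visit 2a or a separate reading classifies: 44.8 in both cases at ρ = 0.8, 54.8 in both at 0.7, and 70.7 against 70.8 at 0.5.

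**Effect of the fix.** If a separate Screening reading classifies, and its error is independent of the Visit 2a error, the expected selection error in the Visit 2a baseline is zero. The sample size does not change. The one-reading misclassification column is unchanged, because one reading still decides.

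**The case against.** **Table 4 may simply be incomplete.** It also marks TBUT N at Visit 1 although criterion 7 in section 7.1.1 requires it at Screening, and it omits the 1-hour visit listed in the Synopsis. No sentence names the classifying reading. A Screening TER could have been intended and left out. This stands as a limit: shared use of the reading is inferred from the schedule. It does not remove the point, because the schedule and the criteria disagree and a site following Table 4 would classify on the baseline.

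**The primary comparison is safe.** A reader might infer that the drop comparison is biased, or that the drop used first carries extra error. The documents do not support either. Order is randomised, each participant receives all three drops, the endpoint in section 6.2 is a difference between drops after instillation with no baseline adjustment stated, and the calculations above show neither effect.

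**The 20/20 split.** A reader might infer that the split cannot be managed at all. The target is only approximate, section 7.3.4 does not exclude later replacement, and Table 4 rechecks the entry criteria at Visit 2a, where a full group could be closed. What stands is that group is unknown until after the run-in. If nothing is steered, the chance of 18 to 22 EDE among 40 is 57% when the true share is 50%, 29% at 40% or 60%, and 3% at 30%.

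**The model simplifies the rule.** Classification uses both eyes and a Schirmer tie-break, with three measurements per eye under each eye condition (section 11.2). Averaging within a session reduces within-session error but not day-to-day variation. If day-to-day variation dominates, the 15-minute artefact is smaller and the 4-week artefact larger.

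**Classifying after a common run-in has merit.** Marketed artificial tears may be in use up to Screening (section 7.1.2), and two weeks on one product standardises that. This is a real cost of the fix.

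**Conclusion.** The concern holds for within-group change from baseline in period 1 and for the EDE versus non-EDE comparison of change. The size is about 8 to 20 g/m²/h in each group in period 1, or 3 to 7 per drop averaged over periods. It rests on SD 50, assumed reliability of 0.8 to 0.5, a mean at the cut-off, a single-reading rule, and Table 4 being followed as printed. The repeatability of TER is the main unknown.

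These figures should not be set against the design difference of 36, which is a contrast between drops that this artefact does not shift. Nor should a reader conclude that moving classification to Screening corrects misclassification: 15% to 25% would still be in the wrong group under the same assumptions. The point is a worthwhile, inexpensive improvement and does not threaten the primary result.

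**What to change.** - In Table 4, set tear evaporation rate to Y at Visit 1. Assign EDE or non-EDE from that reading, using the Schirmer score and eye photograph already taken there.
- State that the Visit 2a pre-drop reading serves only as the period-1 baseline.
- Confirm the cut-off and give its unit before the first participant is screened. The approximate 20/20 target can then be tracked from Screening.
- Reconcile Table 4 with section 7.1.1, including the TBUT row at Visit 1.

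The cost is one more Vapometer measurement, at an existing visit with equipment the site already has, and classification on habitual tears before the common run-in. If misclassification is also to be reduced, classify on the mean of two readings, neither of them the Visit 2a baseline. Under the assumptions above that lowers it to 11% to 20%.
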